11.2 Subject Accountability

Analysis Set Disposition

The number (percent) of subjects in each of the Analysis Subsets detailed in [Section 7](#) will be summarized.

During the Run-In Period

The subject disposition for the run-in period will be summarized descriptively for all subjects enrolled in the run-in period, and will include the number (percent) of subjects who

- are enrolled
- are dosed with open-label etanercept and methotrexate
- complete the 24-week open-label run-in period
- discontinued prematurely and their reasons for discontinuation.

After Randomization

The subject disposition will be summarized descriptively for all randomized subjects by randomized treatment group, and will include the number (percent) of subjects who

- are randomized
- are dosed with investigational product
- complete investigational product
- complete the study
- discontinued prematurely and their reasons for discontinuation.

11.3 Important Protocol Deviations

Important Protocol Deviation (IPD) categories are defined by the study team before the first subject's initial visit and updated during the IPD reviews throughout the study prior to database lock. These definitions of IPD categories, subcategory codes, and descriptions will be used during the course of the study.

11.4 Demographic and Baseline Characteristics

Subject demographic and disease characteristics at enrollment will be summarized descriptively for all subjects in the run-in period.

Subject demographic and baseline disease characteristics at randomization will be summarized descriptively for all subjects in the double-blind treatment period by randomized treatment group.

11.5 Efficacy Analyses

All efficacy analyses will be conducted using the PAS, unless otherwise specified.

11.5.1 Primary Efficacy Endpoint

11.5.1.1 Primary Analysis of Primary Estimand

The primary analysis of the primary estimand as defined in [Section 4.1.1](#) will be performed using the PAS. The primary endpoint is defined in [Section 6.2](#). When an endpoint cannot be derived due to missing SDAI assessment, a subject will be assumed to have not achieved the outcome, that is, Non-Responder Imputation (NRI).

The treatment effect for SDAI remission at Week 48 will be tested using a chi-squared test at significance level of 0.05. Difference in proportions and a 95% CI will be provided comparing etanercept monotherapy with methotrexate monotherapy.

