### **5.1 Randomization/Treatment Assignment**

Subjects who meet Part 2 eligibility criteria will be randomized to receive etanercept plus placebo for methotrexate, methotrexate plus placebo for etanercept or etanercept plus methotrexate in a 2:2:1 ratio via IXRS.

Assignment to the treatment arms will be based on a computer-generated randomization schedule prepared by Amgen before the start of the study. Each randomized subject will receive a single, unique randomization number via IXRS at randomization. The randomization date is to be documented in the subject's medical record as registered in the IXRS.

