### 10.5.3 Secondary Efficacy Endpoints

- Simplified Disease Activity Index remission ( $\leq 3.3$ ) at week 48 for the etanercept plus methotrexate treatment arm will be compared to the methotrexate monotherapy arm using the chi-square test and will be presented with nominal p-values only (eg, no adjustment for multiplicity will be done).
- The proportion of subjects achieving SDAI remission, SDAI continuous score and SDAI change from baseline at all study timepoints will be summarized by treatment group. DAS28-ESR, DAS28-CRP and CDAI and their changes from baseline will be also summarized at all study timepoints by treatment group. Proportion of subjects achieving Boolean remission will be tabulated at all study timepoints by treatment group. Proportion of subjects with disease worsening (defined as an SDAI  $> 3.3$  and  $\leq 11$  during two consecutive visits at least 2-weeks apart or SDAI  $> 3.3$  and  $\leq 11$  on three or more separate visits or SDAI  $> 11$  after randomization) as well as time to disease worsening will be evaluated.
- In subjects that receive rescue treatment during the double-blind treatment period time to recapture of SDAI remission after starting rescue treatment will be analyzed. Additionally, the proportion of subjects who recapture SDAI remission at week 48 will be summarized.

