3.2 Sample Size

The sample size was determined from a hypothesis of superiority of etanercept monotherapy over methotrexate monotherapy. The proportion of subjects achieving SDAI remission after 52 weeks of double-blind treatment in the PRESERVE and COMET studies was used to estimate the treatment effects. PRESERVE was a two-period study conducted in subjects with RA who had moderate disease activity despite a stable dose of oral methotrexate for a minimum of 8 weeks at the time of screening. Among all subjects who were in SDAI remission at both week 28 and week 36 (the last two visits of the open-label run-in period), the proportion of subjects who were still in remission after the 52-week double-blind period was 86.1% and 38.1% for the etanercept plus methotrexate therapy and methotrexate monotherapy treatment groups, respectively. COMET was a two-period study conducted in subjects with active early RA. Among all subjects who received etanercept plus methotrexate therapy in Period 1 and were in SDAI remission at week 52, the last visit of Period 1, the proportion of subjects who were in still in remission after the 52-week double-blind Period 2 was 78.3% and 72.4%, respectively, for the etanercept plus methotrexate therapy and etanercept monotherapy treatment groups. Given key differences noted in this study, including the sustained period of remission prior to withdrawal, the response rate in the methotrexate monotherapy arm is approximated to be higher at 50%, with the response

rate in the etanercept monotherapy arm at approximately 72%. It is expected that compared to PRESERVE, subjects in the current study will have more stable disease at the time of randomization. Namely, subjects must be in very good disease control for 6 months prior to study entry and must be in SDAI remission at the end of a 24-week open-label run-in period.

The sample size is based on the adequacy to evaluate the efficacy of etanercept monotherapy compared to methotrexate monotherapy as measured by the primary endpoint of SDAI remission at week 48 at a significance level of 0.05. The sample size was also ensured to be sufficient to evaluate the efficacy of the etanercept plus methotrexate treatment arm compared to methotrexate monotherapy. Based on a two-sided chi-square test with 90% power, 100 subjects per arm are required at randomization.

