4.2 Planned Covariates

The following baseline covariates will be considered to assess their influence on the primary and secondary endpoints:

- age (years) (continuous)
- sex (male, female)
- race (Caucasian, non-Caucasian)
- ethnicity (Hispanic or Latino vs Non-Hispanic or Latino)
- disease duration (in years)
- baseline methotrexate dose (continuous)
- additional covariates will be evaluated (baseline methotrexate dose [<15 mg / ≥ 15 mg], smoking [never, former, current])

The rationale for inclusion of baseline methotrexate dose [<15 mg / ≥ 15 mg] and smoking status is provided in [Section 12](#).

Subgroup analyses, which would be considered exploratory, may be performed if an examination of the above covariates suggests that any treatment difference for the primary and secondary endpoints depends on any baseline covariates.

5. Hypotheses and/or Estimations

There are two clinical hypotheses. First,

Etanercept monotherapy is superior to methotrexate monotherapy for maintaining remission in subjects with RA who were on etanercept plus methotrexate therapy as measured by the proportion of subjects who maintain SDAI remission ($SDAI \leq 3.3$) at week 48.

Specifically, the null (H_0) and alternative (H_1) hypotheses are defined as follows:

H_0 : The difference in proportion of subjects who maintain SDAI remission at week 48 in the etanercept monotherapy arm and in that of the methotrexate monotherapy arm = 0

H_1 : The difference in proportion of subjects who maintain SDAI remission at week 48 in the etanercept monotherapy arm and in that of the methotrexate monotherapy arm $\neq 0$.

Second,

Etanercept and Methotrexate combination therapy is superior to methotrexate monotherapy for maintaining remission in subjects with RA who were on etanercept plus methotrexate therapy as measured by the proportion of subjects who maintain SDAI remission ($SDAI \leq 3.3$) at week 48.

Specifically, the null (H_0) and alternative (H_1) hypotheses are defined as follows:

H_0 : The difference in proportion of subjects who maintain SDAI remission at week 48 in the etanercept and methotrexate combination arm and in that of the methotrexate monotherapy arm = 0

H_1 : The difference in proportion of subjects who maintain SDAI remission at week 48 in the etanercept and methotrexate combination arm and in that of the methotrexate monotherapy arm $\neq 0$.

6. Definitions

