10.6 Distributional Characteristics

The Chi-squared test with continuity correction allows for analysis of categorical endpoints even when some or all contingency cells have less than 5 subjects. The t-test used for continuous endpoints assumes that the means of two independent populations follow normal distributions. With all three treatment arms having more than 30 subjects, this assumption is fair per the central limit theorem. When standard deviations are statistically significantly different as identified by an F-test with p-value less than or equal to 0.05, the Satterthwaite approximation is used.

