11.1 General Considerations

The primary analysis will be performed after all subjects have completed the Week 48/ET assessment and the 30-day safety follow-up period and all data have been finalized.

Subject disposition, demographics, and baseline disease characteristics will be summarized descriptively by randomized treatment group.

For categorical endpoints, descriptive statistics will report frequency and percentage. For continuous endpoints, descriptive statistics will include the number of observations, mean, standard error or standard deviation, median, minimum, and maximum.

The statistical test for the primary efficacy endpoint will have a significance level of 0.05. Non-responder imputation will be employed for the missing values of the primary endpoint.

For continuous secondary endpoints, t-tests will compare 1) etanercept monotherapy vs methotrexate monotherapy, and 2) etanercept and methotrexate combination therapy vs methotrexate monotherapy. No multiplicity adjustments will be made.

For binary secondary endpoints, Chi-squared tests with continuity correction will compare 1) etanercept monotherapy vs methotrexate monotherapy, and 2) etanercept and methotrexate combination therapy vs methotrexate monotherapy. No multiplicity adjustments will be made.

For time-to-event secondary endpoints, the number of subjects achieving the event and the number of subjects censored as defined in [Section 6.4](#) will be provided.

Kaplan-Meier (KM) curves, estimates, and 95% CIs will be provided by treatment group. A two-sided log-rank test incorporating treatment group will evaluate 1) etanercept monotherapy vs methotrexate monotherapy, and 2) etanercept and methotrexate combination therapy vs methotrexate monotherapy. Median time-to-event will be provided for each of the treatment arms.

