SDAI remission (≤ 3.3) at week 48	
Count (percentage) of subjects achieving SDAI remission as defined by SDAI_remission_maintenance detailed in Section 6.2 at Week 48 for the PAS.
 
A chi-squared test comparing etanercept plus methotrexate combination arm and methotrexate monotherapy using the PAS.
 
Subjects who have a missing SDAI_remission value will be considered as non-responders. Nominal p-values will be provided.
	
Observed_SDAI_remission using as observed approach as detailed in Section 6.5 (missing data will be excluded).
 
Multiple imputation method: impute SDAI values when missing and after rescue for randomized subjects. The composite SDAI values will be imputed rather than its components.

SDAI score and change from baseline at all measured timepoints	
Summary statistics for SDAI score and change from baseline at each Analysis Visit for the PAS.
 
T-test comparing etanercept monotherapy vs methotrexate monotherapy
 
T-test comparing etanercept and methotrexate combination therapy vs methotrexate monotherapy
	
DAS28-ESR and change from baseline at all measured timepoints	
Similar analysis as for SDAI score and change from baseline at all measured timepoints
	

Table 1. Primary and Secondary Endpoints Summary Table

Endpoint	Primary Analysis Method	Sensitivity/Exploratory Analysis
Secondary Endpoints (Continued)		
DAS28-CRP and change from baseline at all measured timepoints	Similar analysis as for SDAI score and change from baseline at all measured timepoints	
CDAI and change from baseline at all measured timepoints	Similar analysis as for SDAI score and change from baseline at all measured timepoints	
SDAI remission (≤ 3.3) at all measured timepoints	Count (percentage) of subjects achieving SDAI remission as defined by SDAI_remission_maintenance detailed in Section 6.5 for the PAS. Chi-squared test comparing etanercept monotherapy vs methotrexate monotherapy Chi-squared test comparing etanercept and methotrexate combination therapy vs methotrexate monotherapy	
Boolean remission at all measured timepoints	Observed count (percentage) of subjects achieving Boolean remission at each Analysis Visit for the PAS. Boolean remission using 28-joint-count, 28-joint-count + feet and ankles, and 66/68 joint count will be assessed. Chi-squared test comparing etanercept monotherapy vs methotrexate monotherapy Chi-squared test comparing etanercept and methotrexate combination therapy vs methotrexate monotherapy	

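### The SAP does not say whether the primary chi-square is continuity-corrected, and it tests the disease-activity scores without baseline adjustment: a minor matter of specification and precision, not bias.

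*SAP*

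**What the plan says.** **Primary test.** SAP 11.5.1.1: "The treatment effect for SDAI remission at Week 48 will be tested using a chi-squared test at significance level of 0.05". SAP Table 1 and Protocol 10.5.2 likewise name a chi-square test and do not mention a correction.

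**Correction elsewhere in the SAP.** Section 10.6: "The Chi-squared test with continuity correction allows for analysis of categorical endpoints", with no limit to secondary endpoints. Section 11.1: "For binary secondary endpoints, Chi-squared tests with continuity correction will compare 1) etanercept monotherapy vs methotrexate monotherapy". Section 11.5.2 and Table 1 then name a plain chi-squared test for those same endpoints. One of them is combination v methotrexate at Week 48, which 11.5.2 says should parallel the primary analysis.

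**Sample size.** SAP 3.2: "Based on a two-sided chi-square test with 90% power, 100 subjects per arm are required at randomization". The assumed rates are approximately 72% and 50%.

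**Scores.** SAP Table 1 lists "Summary statistics for SDAI score and change from baseline at each Analysis Visit for the PAS", followed by t-tests of each etanercept-containing arm against methotrexate. DAS28-ESR, DAS28-CRP and CDAI are handled the same way. Protocol 10.5.3 says only that "SDAI continuous score and SDAI change from baseline at all study timepoints will be summarized by treatment group"; it names no test.

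**Covariates.** SAP 4.2: "The following baseline covariates will be considered to assess their influence on the primary and secondary endpoints". None is entered in a treatment comparison. On allocation, Protocol 5.1 says "Assignment to the treatment arms will be based on a computer-generated randomization schedule prepared by Amgen before the start of the study" and names no stratification factors.

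**The concern.** The primary comparison is the only one that carries the 0.05 significance level, so its test statistic should be fixed to the last detail before unblinding. As written, two programmers could follow the SAP and report different primary p-values. One would run the plain test named in 11.5.1.1. The other would take 10.6 to cover every categorical endpoint and apply the correction. A borderline result could be significant under one reading and not under the other.

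For the scores, a raw-score test ignores baseline and a change test uses it only by subtraction. Running both gives two p-values per score, visit and comparison, with no rule for which to read. One baseline-adjusted analysis would generally be at least as precise as either and would give a single answer.

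**Working it through.** **1. Reproducing the plan's 100 per arm.** Inputs from SAP 3.2 and Protocol 10.2: p1 = 0.72, p2 = 0.50, difference 0.22, two-sided alpha 0.05 (z = 1.960), power 90% (z = 1.282). Mean rate 0.61.

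- Pooled, uncorrected: n = [1.960·√(2·0.61·0.39) + 1.282·√(0.72·0.28 + 0.50·0.50)]² / 0.22² = 101.2, so 102.
- Unpooled, uncorrected: n = (1.960 + 1.282)²·(0.2016 + 0.25) / 0.22² = 98.04, so 99.
- Continuity-corrected: n' = (n/4)·[1 + √(1 + 4/(n·0.22))]² with n = 101.2 gives 110.1, so 111.

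The stated 100 lies between the two uncorrected answers and 11 below the corrected one.

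**2. Exact behaviour of the two tests.** Enumeration of all binomial outcomes at 100 v 100, rejecting when the statistic exceeds 3.841:

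| Quantity | Uncorrected | Corrected |
|---|---|---|
| Power, 72% v 50% | 89.8% | 86.9% |
| Power, 72.4% v 50% | 90.9% | 88.1% |
| Power, 73% v 50% | 92.3% | 89.9% |
| Smallest n per arm for 90% at 72% v 50% | 101 | 111 |
| Type I error, common rate 0.50 | 5.6% | 4.0% |
| Type I error, common rate 0.61 | 5.1% | 3.6% |
| Type I error, common rate 0.72 | 5.0% | 3.4% |

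The choice is worth 89.8 − 86.9 = 2.9 points of power at the design rates.

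**3. Results on which the two tests disagree.** 64 v 50 responders per 100: p = 0.046 uncorrected, 0.063 corrected. 59 v 45: p = 0.048 and 0.066. At 65 v 50 both reject (0.032 and 0.045), so the zone of disagreement is narrow.

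**4. Scores: ANCOVA against the two t-tests.** Set the follow-up SD to 1, the baseline SD to k, and their correlation to r. Per-subject variances are 1 for the raw score, 1 + k² − 2rk for change, and 1 − r² for ANCOVA. The documents give neither k nor r. I assume k = 0.25, because Protocol inclusion 116 requires SDAI of at most 3.3 at run-in visit 3, within 7 days of Day 1, and r from 0.1 to 0.5.

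| r | ANCOVA / change | ANCOVA / raw |
|---|---|---|
| 0.1 | 0.9900/1.0125 = 0.98 | 0.99 |
| 0.25 | 0.9375/0.9375 = 1.00 | 0.94 |
| 0.3 | 0.9100/0.9125 = 1.00 | 0.91 |
| 0.5 | 0.7500/0.8125 = 0.92 | 0.75 |

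If the two SDs were equal, which is unlikely for SDAI here, the change test would have 2/(1 + r) times the ANCOVA variance: 1.54 at r = 0.3.

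**5. Why a robust variance.** In simulation (20,000 runs per setting), ANCOVA with HC3 variance held type I error at 4.6 to 5.2% for 50 v 100 and 100 v 100. With pooled variance it reached 8.4 to 8.7% at 50 v 100 when the smaller arm's SD was assumed 1.5 times larger.

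**6. Adjusting the primary endpoint.** With one baseline covariate of assumed odds ratio 1.0, 1.25 or 1.5 per SD, a standardised logistic risk difference has variance 1.01, 1.00 or 0.97 of the unadjusted one. Used as the primary test, it would add 0.0, 0.4 or 1.0 points of power.

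**The case against.** **The correction may be settled elsewhere.** SAP Appendix B is headed as code fragments, and its code is absent from the supplied text. It could show the option used. This stands as a caveat: the omission is established only for the text available. The differences among 10.6, 11.1 and 11.5.2 would still need reconciling.

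**The sample size does not prove which test was meant.** A reader might infer that 100 per arm is compatible only with the uncorrected test. It is not: the rate is given as approximately 72%, and at 73% the corrected test has 89.9% power. The uncorrected test is the better fit, no more.

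**A reader might infer that the primary analysis is invalid or biased for want of adjustment.** The documents do not support that. No stratified randomisation is described that the analysis would have to reflect, both forms of the chi-square are acceptable tests, and the plausible gain from adjustment is about 0 to 1 point of power. Larger gains need prognostic strengths that no document supports. Day 1 SDAI is range-restricted and so probably a weak predictor.

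**The scores are secondary, without multiplicity control, and the gain over the change test is 0 to 8% on assumed inputs.** This also stands and limits the grade. What remains is that baseline is already collected and that one test replaces two.

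**The t-test variance rule.** Section 10.6 selects the Satterthwaite version by an F-test, whereas 11.5.2 makes it permissive. Always using Satterthwaite looks better with normal data: at 7 v 50, with the smaller group's SD 1.5 times larger, type I error is about 5% against about 10.5% for the F-test rule. With skewed (exponential) data in the same setting the order reverses, at about 11% against about 9%. Replacing the rule is therefore not shown to be an improvement in small skewed subsets.

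**Conclusion.** A minor point that holds in two parts. First, in the supplied text the primary chi-square is not fully specified, and the SAP's wording on the correction is inconsistent across sections, including for the Week 48 comparison meant to mirror the primary one. The open choice is worth 2.9 points of power at 72% v 50%, and it moves exact type I error between 3.4 to 4.0% and 5.0 to 5.6% for common rates of 0.50 to 0.72. These figures are exact given 100 per arm and the stated rates.

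Second, the unadjusted paired t-tests on the scores cost some precision: nothing to 8% of variance against the change test and 1 to 25% against the raw-score test, under the assumed SD ratio of 0.25 and correlations of 0.1 to 0.5. If the restricted baseline is only weakly prognostic, the gain is close to nothing.

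The variance rule for t-tests and an adjusted risk difference for the primary endpoint are optional refinements.

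**What to change.** Before unblinding:

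1. State in SAP 11.5.1.1 that the primary chi-square is uncorrected, and align 10.6, 11.1, 11.5.2 and Table 1 with that choice. Cost: a few sentences, and acceptance of type I error up to about 5.6% at a common rate of 0.50.
2. Test SDAI, DAS28-ESR, DAS28-CRP and CDAI once per visit and comparison by ANCOVA with the score's own baseline value and HC3 robust variance. Keep raw score and change as descriptive summaries. Edit 11.1, 11.5.2 and Table 1, not only Section 12. Cost: modest programming, no new data, and no change to a protocol-named test.
3. If the run-in visit 3 value is to stand in for a missing Day 1 value, amend SAP 6.1 (which takes baseline after that visit, except for hematology and chemistry) and 10.3.1 (which rules out imputing baseline). Use the same baseline in the change summaries, so that tests and summaries cover the same subjects.

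Optional: make the variance rule in 10.6 and the wording in 11.5.2 agree. A supportive standardised risk difference adjusted for Day 1 SDAI may be added, but it adds no power to the primary test.

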11.5.1.2 Sensitivity/Exploratory Analyses of Primary Estimand

SDAI remission at Week 48 will be tested using a chi-squared test at significance level of 0.05 using observed cases only.

In addition, multiple-imputation will be implemented to impute SDAI values when missing for randomized subjects. SDAI values after rescue are also set to missing and imputed in this analysis. The composite SDAI values will be imputed rather than its components. A chi-squared test will compare the resulting values under the etanercept monotherapy arm and the methotrexate monotherapy arm.

